3. HRSD >=18

3. Data from IRB 7489

4. Willing to and capable of providing informed consent and complying with study procedures.

4. Clinical interview

Create or insert table to describe the exclusion criteria and methods to ascertain them

Exclusion criteria:

Method of ascertainment:

1. History of allergic or adverse reaction to escitalopram and duloxetine

1. Clinical interview, data from IRB 7489

2. Non-response to adequate trial of escitalopram (at least 4 weeks at dose of 20mg) and duloxetine (at least 4 weeks at dose of 60mg) during the current episode

2. Clinical interview, data from IRB 7489

3. Current treatment with psychotherapy, antidepressants, or other psychotropic medications.

3. Clinical interview, data from IRB 7489

Waiver of Consent/Authorization

Indicate if you are requesting any of the following consent waivers

Waiver of consent for use of records that include protected health information (a HIPAA waiver of Authorization)

No

Waiver or alteration of consent

No

Waiver of documentation of consent

Yes

Waiver of parental consent

No

Consent Procedures

Is eligibility screening for this study conducted under a different IRB protocol?

Yes

Indicate NYSPI IRB #

7489

Describe Study Consent Procedures

Participants who complete IRB 7489, meet the study selection criteria and agreed to be contacted in the future will be approached by a study clinician, Psychiatrist (MD), or a Psychiatric Nurse Practitioner (NP) authorized to obtain patient consent. Study clinicians who obtain consent for this study are licensed Doctors of Medicine (MD) and/or Psychiatric Nurse practitioners (NP) in the State of New York. Participants may be approached on the day of their final study visit for protocol IRB 7489 or may be contacted by phone.

Participants who have a computer/smartphone/tablet access will be asked to provide verbal consent to participate in the interviews, and verbal consent will be documented. The participant will receive a consent form and HIPAA form via REDCap for e-consent, if a participant has access to a computer and email. The Clinician (MD or NP) will explain to the participants their diagnosis with MDD, symptom level, and the options for treating this will be discussed (including not treating it). The clinician (MD or NP) will discuss the risks, benefits, and alternatives to treatment with escitalopram or duloxetine and allow the participant the opportunity to ask questions. This will take place via a HIPAA compliant video conferencing platform,

Webex. The consent process will also include a discussion and explanation of Webex and will address any concerns the participant may have, such as access to private space in which to take calls, or accessibility at home to adequate devices, cell signal, or WIFI. If a participant does not have the appropriate technology in order to complete e-consent through REDCap, than a research staff member will verbally consent the participant and it will be documented. These participants will be mailed a copy of the consent form and HIPAA form. A consent procedure note will include all information discussed with the participants regarding the remote consent process, procedures and also the risk involved in traveling for in-person visits during the COVID-19 pandemic.

Indicate which of the following are employed as a part of screening or main study consent procedures

✓ Consent Form

Waiver of Documentation of Consent

Would the consent form signature be the only link between the subject’s identity and the research data?

No

Is breach of confidentiality the main study risk?

No

Is consent for this research procedure ordinarily not required outside of the research context? Explain

We plan to consent potential participants on the last study visit for protocol #7489. Participants who have already completed their last study visit will be contacted by a study clinician (MD/NP), authorized to obtain consent, who will explain the study procedures and answer any questions that the participant may have via a HIPAA compliant Video conferencing platform, Webex. If the subject agrees to participate, they will be sent an online link using REDCap to access the consent form. We are requesting a waiver of documentation of consent for participants who do not have the technology to sign the consent via REDCap. Participants will be asked to sign a paper consent form when they arrive to clinic for the in person visit.

Persons designated to discuss and document consent

Select the names of persons designated to obtain consent/assent

[name]

[name], MD

[name]

[name], MD

[name], MD

Type in the name(s) not found in the above list

Study Procedures

Describe the procedures required for this study

I attest to follow the COVID-19 Safety Guidelines for Columbia Psychiatry and NYSPI Re-Entry outlined in the NYSPI Director's June 1st memo, which include but are not limited to:

- Infection Control/PPE –Guidelines
- Research participants will only come on-site if absolutely necessary for study procedures.
- No volunteers/externs on-site during Stage 1.
- Clinical research teams will screen their participants for COVID symptoms (night before and day of onsite visit, documenting this in the chart), and escort them in and out of the building.
- COVID/COVID-like symptoms in participants will be reported to the IRB via PRISMA as an SAE.

1. Following consent, the participant will be begun on either escitalopram 10mg or duloxetine 30mg. The default medication will be escitalopram. Subjects will begin escitalopram 10mg, continue this dosage for 4 weeks, then if the HRSD >7 at Week 4, he/she will have their dosage increased to 20mg for the remainder of the 8 week study. Participants who have not responded to or not tolerated escitalopram in the current depressive episode will be started on duloxetine. They will take 30mg of duloxetine for the first 2 weeks, then, **contingent on clinical assessment that the 30mg dose is sufficiently well tolerated**, be increased to 60mg for the **remaining 6 weeks** of the study. Participants will be provided with the study medication during the Week 0 (baseline) in person visit. During the week 4 (virtual) visit, participants **taking escitalopram** will be sent the study medication directly to their home via Fedex. **This will be done during the week 2 (virtual) visit for participants taking duloxetine.** If significant worsening occurs and/or the participant wishes to be seen in person for the week 4 **or week 2** visit, they will be provided with the study medication onsite.

Study Visits will occur in person/virtually as outlined below:

- Week 0: In-person
- Week 2: Virtual
- Week 4: Virtual
- Week 6: Virtual
- Week 8: In-person

2. Subjects unable to tolerate the higher dose of study medication will have their dose reduced to the previously tolerated dose. Subjects unable to tolerate the beginning dose of study medication will be tried (if possible given their history) on the other study medication. Participants unable to tolerate the beginning dose of either study medication will be dropped from the study and enter post protocol open treatment.

3. Subjects will have telephone/video-conference visits via a telephone and/or a HIPAA compliant video conferencing platform, Webex with the research assistant and study clinician every two weeks. The RA will check Hamilton Rating Scale for Depression (HRSD) and Hamilton Anxiety Rating Scale (HARS) at each call. The study clinician will then evaluate the participant and complete the Clinical Global Impressions (CGI) Severity and Improvement. If the participant requests or significant clinical worsening in the

judgement of the study clinician occurs, then the participant will be brought to NYSPI for in person evaluation.

4. At Week 8 study endpoint, participants will return to the Clinic on Aging, Anxiety, and Mood Disorders (CAAM) and the Anxiety Disorders Clinic (ADC) for HRSD, HARS, CGI Severity and Improvement, PCL-5, and CAPS-5. In addition, repeat neuropsychological testing and physical function assessment (the same tests from baseline in IRB 7489) will be performed. These include frailty characteristics assessed from the Fried model: unintentional weight loss (10 lbs or 5% of body weight in the past year), self-reported exhaustion, weakness (grip strength), slow walking speed, and low physical activity. Exhaustion will be dichotomized as yes/no using a physical fatigability cutoff score of >10 on the Pittsburgh Fatigability Scale (PFS). Grip Strength is measured using a Jamar dynamometer with maximum grip strength measured over 3 trials. Gait will be assessed as walking speed in m/s on a GaitRITE walkway. Physical activity is assessed via a measure of weekly kilocalories (kcal) derived from the 18-item Minnesota Leisure Time Physical Activity Questionnaire. Function will be assessed using the Short Physical Performance Battery (SPPB), the 36-item self-report World Health Organization Disability Assessment Schedule 2.0 (WHODAS2), and the self-report Measure of Everyday Cognition (ECog). Cognitive scales will include Coding from WAIS-III, Trail Making Test Part A, Pattern and Letter Comparison Tests, Rey AVLT, in addition to testing with the NIH Toolbox for cognition supplemented by NIH EXAMINER.

5. As in IRB 7489, throughout all assessment procedures, the following safety plan will be in place to mitigate the risk that subjects will become frustrated or upset. First, a discussion will be had with participants as to the schedule of assessments. Flexibility will be maintained insofar as possible, such that assessments will be scheduled according to subjects' preferences (e.g., all at one time vs. breaking up over multiple sessions). Second, subjects will be offered a 15 minute break after each hour of assessments. Third, subjects will be informed that a study clinician is available should they become frustrated or upset. Upon the subject's request or if the subject appears upset, the research staff member conducting the assessment will stop the assessment and contact the study clinician. The study clinician will come assess the subject and make a determination of whether or not assessment may proceed or whether clinical treatment is indicated.

6. Following the 8 weeks of open treatment, participants will be eligible for 3 months of post protocol open antidepressant treatment. They will continue to receive referrals for PTSD treatment as specified in IRB 7489.

You can upload charts or diagrams if any

Criteria for Early Discontinuation

Criteria for Early Discontinuation

If a patient discontinues medication due to tolerability problems, ineffectiveness, patient preference, or other reasons, the patient will be dropped out of the study and enter the 3 month long open treatment phase. Appropriate medication options will be discussed with the patient based on their symptoms and history. If the patient wishes, they will be provided referrals for psychotherapy or treatment options outside of our research clinic. No further research measures will be conducted once a patient enters the open treatment phase.

Patients in all treatment cells will be discontinued from the acute treatment phase if there is there is a rating of 6 (much worse) or 7 (very much worse) on the CGI—I for 2 consecutive weeks. Patients may also be discontinued from the study if this is indicated in the clinical judgement of the study physician and/or principal investigator. Patients receiving escitalopram/duloxetine may continue receiving the same medication if clinically indicated after being dropped from the study. No further research measures will be performed on patient dropped from the study.

Patients will be informed that should they experience a crisis or acute symptom worsening between scheduled weekly appointments, they should call their study clinician via the clinic office/research coordinator or the 24 hr doctor on call pager for CAAM. The study physician will evaluate the patient and make appropriate follow up arrangements, which may include activating EMS, calling the relevant mobile crisis team, or scheduling pt for immediate outpatient appointment in the CAAM. Patients in crisis will be assessed immediately and appropriate clinical action taken as above (i.e., those meeting criteria for early discontinuation will be dropped from the study and treated openly).

Blood and other Biological Samples

Please create or insert a table describing the proposed collection of blood or other biological specimens. No additional blood will be drawn over and above what was already drawn for IRB 7489.

Assessment Instruments

Create a table or give a brief description of the instruments that will be used for assessment
Hamilton Anxiety Rating Scale (HARS) 14-item scale: standard measure of anxiety severity in pharmacotherapy studies and has been shown to have good reliability and validity.

--15 minutes

24-item Hamilton Rating Scale for Depression (HRSD): standard measure of depression severity used across diverse patient samples, including PTSD.

--15 minutes

CGI Severity and Improvement: scales measuring the clinician's view of subjects' global functioning.

--1 minute

Digit Symbol test from the WAIS-III: measure of processing speed.

--2 minutes

Pattern and Letter Comparison tests: reliable measures of processing speed.

--4 minutes

Trail Making Test Part A: reliable test of motor speed.

--3 minutes

Selective Reminding Test: test of episodic memory functioning will allow us to identify deficits in episodic memory functioning consistent with a classification of amnesic mild cognitive impairment (aMCI).

--10-15 minutes

NIH-EXAMINER battery: designed to assess executive functions reliably, comprehensively, and efficiently. This battery examines working memory, inhibition, set shifting, fluency, insight, planning, social cognition and behavior.

--1 hour

NIH Toolbox Cognition Battery: brief, diverse, accessible, and psychometrically sound set of 7 computerized instruments that measure 6 ability subdomains important for cognitive health.

--45 minutes

Frailty characteristics: unintentional weight loss (10 lbs or 5% of body weight in the past year), self-reported exhaustion, weakness (grip strength), slow walking speed, and low physical activity.

--10 minutes

Pittsburgh Fatigability Scale (PFS): the only self-report measure of fatigability associated with performance and perceived exertion.

--5 minutes

Minnesota Leisure Time Physical Activity Questionnaire: measure of physical activities, with activity levels < 383 kcal considered frail.

--5 minutes

Posttraumatic Stress Disorder Checklist (PCL-5): 20-item self-report PTSD symptom screening instrument that has been shown to have good internal consistency, strong correlations with other PTSD scales, and high diagnostic efficiency.

--5-10 minutes

Clinician-Administered PTSD Scale for DSM-5 (CAPS-5): The CAPS is a 30-item instrument containing 0- 4 Likert-style item frequency and intensity scales for PTSD symptoms, with subscales for intrusion, avoidance, and hyperarousal symptom clusters, and associated affective features.

--45 minutes

Please attach copies, unless standard instruments are used

Off label and investigational use of drugs/devices

Choose from the following that will be applicable to your study

Research Related Delay to Treatment

Will research procedures result in a delay to treatment?

No

Treatment to be provided at the end of the study

Post-protocol open treatment for 3 months as described above. Following that, patients will receive appropriate referrals, which may include further research studies.

Clinical Treatment Alternatives

Clinical treatment alternatives

Patients could opt to be treated for their depression with other antidepressant medications or psychotherapy. They could also opt not to undergo treatment.

Risks/Discomforts/Inconveniences

Risks that could be encountered during the study period

Patients may experience:

1. Interview, emergencies, and possible suicidal ideation: Subjects may experience discomfort during the clinical interview and evaluations when discussing symptoms and current life events.
2. Antidepressant Side Effects: Side effects will be assessed at each planned visit and if needed through additional or unscheduled contacts. Side effects of these medications include somnolence, diarrhea, nausea, impaired ejaculation, impotence, dry mouth, tremor, and sweating. Escitalopram and duloxetine have black box warnings regarding an increased risk for suicidal thinking and behavior in adolescents and young adults (less than 24 years old) given the drug. Both drugs are of unknown risk to a fetus.
3. Breach of confidentiality: There is the potential risk of breach of confidentiality of clinical information.
4. Due to the COVID-19 pandemic, the additional risk of contracting the virus with any human interaction is present, due to the method of how the virus is transmitted.

Describe procedures for minimizing risks

1. Interview, emergencies, and possible suicidal ideation: The study coordinators are experienced and skilled in interviewing depressed subjects. Half-way through the initial assessment, the coordinator will ask the subject if they would like to take a break, and this will be provided if desired. A study clinician will be

available during all aspects of the assessment if there are any questions or problems. In addition, should the subject express suicidal ideation at any time during the interview, the study clinician will be contacted immediately to assess the subject and to determine the appropriate course of action. Options for addressing suicidal ideation will include contacting the individual's mental health caregiver, referring for urgent (same day) evaluation and treatment in an outpatient clinic, or emergency room evaluation and hospitalization. Similar practices will be used for other emergencies, including but not limited to psychosis, homicidal or violent thoughts, or an acute change in a subject's physical status.

2. Antidepressant Side Effects: We will attempt to minimize side effects by slow dosage titration and allowance for dose reduction if needed. We will withdraw subjects from the study if they cannot tolerate the lowest dose of escitalopram or duloxetine. Since the proposed study will enroll subjects aged 50 and older, the particular risks mentioned above are not expected to be applicable. Regardless, all subjects will be asked to tell their doctors immediately if they experience suicidal thoughts, and menopausal status and date of last menstrual period will be documented in all female participants.

3. Breach of confidentiality: [name] has extensive experience as a clinical investigator in dealing with sensitive information and assuring that data is adequately protected. Safeguards to protect confidentiality include locked records and firewalls around password-protected electronic data, and all study data being coded, with the key linking the code with a subject's identity being kept in a separate, locked file. Of note, any and all videoconferencing sessions will be hosted via WebEx-- secure, HIPAA-compliant video conferencing. For participants with email access, self-report measures will be sent via encrypted email.

4. Specifically, for in-person visits to NYSPI, individuals are at increased risk for exposure to COVID-19 both in transit to NYSPI as well as during their time at NYSPI. Procedures are in place to minimize this risk. We plan to offer car transportation subject to a maximum of \$50 each way, which minimizes exposure to public transportation for those participants. At NYSPI, personal protective equipment such as masks will be utilized at all times both by staff and participants, and social distancing will be adhered to when possible. Screen shields between patient and staff will be used during neuropsychological testing to further minimize exposure risk.

Methods to Protect Confidentiality

Describe methods to protect confidentiality

All records of the participating subjects will be kept in a locked room with access provided only to staff members. Records will be available to research staff, and to Federal, State and Institutional regulatory personnel (who may review as part of routine audits). Patients' names will be linked with code numbers in a password protected file to which only the research assistant has access. Only these code numbers will appear on all pill bottles and paper measures collected during study. All data collected will be kept confidential and used for professional purposes only. Publications using these data will be done in a manner that protects the subjects' anonymity. All electronically stored data will be accessible by password known only to the principal investigator and research assistants for the study. Due to the implementation of virtual visits, additional measures to protect patient confidentiality will be employed. These include using only

secure platforms for virtual calls (WebEx, etc.), the use of headphones during virtual calls, and not including any PHI on assessment forms that are to be scanned and sent to research coordinators after patient completion for weekly visits.

Will the study be conducted under a certificate of confidentiality?

No

Direct Benefits to Subjects

Direct Benefits to Subjects

No direct benefit to subjects are guaranteed, but patients who are not currently in treatment and are experiencing depressive symptoms will receive a medication proven effective for their condition and may achieve remission from the depression as a result of participating in the study.

Compensation and/or Reimbursement

Will compensation or reimbursement for expenses be offered to subjects?

Yes

Please describe and indicate total amount and schedule of payment(s).

Include justification for compensation amounts and indicate if there are bonus payments.

Subjects will receive reasonable compensation for the time and effort associated with the completion of study visits. Participants will receive \$25 for each biweekly visit (Week 0, 2, 4, 6) for a total of \$100. Participants will receive \$100 for completion of the end of treatment assessments (Week 8).

Thus, the maximum compensation that a participant may receive for completion of all study visits will be \$200. This money will be paid by gift card or check at the conclusion of each study visit.

References

References

Uploads

Upload copy(ies) of unbolded Consent Form(s)

Upload copy(ies) of bolded Consent Form(s)

Upload copy(ies) of the HIPAA form

PTSD Treatment_HIPAA_Authorization_1.8.21.pdf

Upload any additional documents that may be related to this study

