Indicate which of the following populations will be included in this research

- ✓ Adults over 50

Research Support/Funding

Will an existing internal account be used to support the project?

Yes

Describe internal account

[name] University Irving Scholar account

Is the project externally funded or is external funding planned?

No

Study Location

Indicate if the research is/will be conducted at any of the following

✓ NYSPI

This protocol describes research conducted by the PI at other facilities/locations

No

Lay Summary of Proposed Research

Lay Summary of Proposed Research

In our ongoing studies of Posttraumatic Stress Disorder (PTSD) in older adults, we have found that older adults with PTSD frequently meet criteria for comorbid Major Depressive Disorder (MDD). Moreover, relative to trauma-exposed healthy controls (TEHCs), elders with PTSD manifest executive function deficits, fatigability, and mobility and physical function deficits that are consistent with what we have observed in depressed older adults. Yet, we have found that very few older adults with combined PTSD/MDD have received appropriate antidepressant treatment for their condition.

These findings give rise to the questions of (1) how effective is antidepressant treatment for depressive symptoms in the context of PTSD/MDD and (2) are cognitive and physical function deficits in PTSD/MDD patients reversible with effective antidepressant treatment?

Participants who recently completed IRB 7489 and who sign consent to participate in this open treatment study will be treated for 8-weeks with antidepressant medication. Participants will be seen in person for the week 0 (baseline) visit, where they will complete baseline testing. Participants will meet with research assistants and clinicians every two weeks virtually, via a HIPAA compliant video platform, Webex. They will then come in person for the final study visit, week 8. Week 8 will be conducted in person and will consist of repeat baseline testing. This will be the second study visit conducted in person, unless a significant clinical worsening occurs and/or the participant wishes to be seen in person for a visit. Following the 8 weeks, participants will be eligible for 3 months post protocol open treatment and will continue to receive referrals for PTSD treatment.

Background, Significance and Rationale

Background, Significance and Rationale

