In our ongoing IRB #7489, we hypothesize that chronic PTSD, over and above other contributing factors, accelerates biological aging in the brain and body, leading to adverse behavioral consequences such as frailty and cognitive decline. To test these hypotheses, 150 individuals are being recruited who are aged ≥ 50 and diagnosed with PTSD. A control group of 150 age-, sex-, and trauma exposure-matched subjects without PTSD are being recruited and assessed. Included subjects undergo comprehensive neuropsychological assessment and cerebral blood volume functional magnetic resonance imaging (CBV-fMRI) to assess regional hippocampal metabolic activity and function. Structural MRI is performed to quantify WMH, regional brain volume, and cortical thickness, while resting state fMRI measures functional connectivity within hippocampal networks. PTSD subjects and controls are compared on measures of aging within the following domains: neural (DG CBV, WMH, morphology), cognitive (processing speed, memory, executive function, pattern separation), somatic (peripheral inflammatory markers, leukocyte telomere length, and measures of oxidative stress), and behavioral (grip strength, gait speed, fatigue levels). By elucidating the interaction of chronic PTSD with aging processes, data from this project may contribute to the development of rationally designed, personalized, and age-appropriate novel treatments.

Interim analyses of PTSD subjects in this study demonstrate a high degree of comorbidity with MDD. Among participants with PTSD enrolled to date, 67.1% meet criteria for MDD and mean Hamilton Rating Scale for Depression (HRSD) is 18.1. The most prominent cognitive differences observed to date in our study between PTSD and TEHC subjects is executive dysfunction, which is common in late life depression. PTSD subjects have dramatically increased fatigability and prevalence of frailty criteria compared to TEHCs, abnormalities which are also frequently seen in our older MDD samples. Yet, we have found that less than 25% of these individuals are currently receiving an adequate dose and duration of first-line pharmacotherapy for MDD, while only one third report any past medication treatment. These data raise the question of whether patients with combined PTSD/MDD could benefit from adequate antidepressant medication treatment and to what degree their cognitive and physical function deficits would be reversible with this therapy.

Specific Aims and Hypotheses

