Specific Aims and Hypotheses

Aim 1. To study the effectiveness of antidepressant medications to treat depressive symptoms in older adults with PTSD/MDD.

Hyp 1: A significant improvement in depressive symptoms will be observed, and response rates to open antidepressant medication treatment in this population will be greater than 50%.

Aim 2: To evaluate change in cognition and physical function following antidepressant medication treatment.

Hyp 2: As compared to non-responders, responders to antidepressant treatment will demonstrate significantly greater improvement in executive function (NIH Toolbox) and gait speed.

Description of Subject Population

Sample #1

Specify subject population

Participants in IRB 7489 with combined PTSD and MDD

Number of completers required to accomplish study aims

20

Projected number of subjects who will be enrolled to obtain required number of completers

25

Age range of subject population

50 years and older

Gender, Racial and Ethnic Breakdown

We anticipate the sample will be composed of approximately 60% women and 40% men.

Racial/ethnic group: On the basis of previous depression studies conducted in the Clinic for Aging, Anxiety, and Mood Disorders, it is anticipated that the sample will be composed of approximately 75% Caucasian, 15% African American, and 10% Hispanic subjects.

Description of subject population

The proposed study will enroll 25 outpatients who are (1) participants in IRB 7489, (2) diagnosed with DSM 5 MDD, (3) have HRSD ≥ 18 , and (4) are willing to and capable of providing informed consent and complying with study procedures. Participants will be excluded for (1) history of allergic or adverse reaction to escitalopram and duloxetine, (2) non-response to adequate trial of escitalopram (at least 4 weeks at dose of 20mg) and duloxetine (at least 4 weeks at dose of 60mg) during the current episode, or (3) current treatment with psychotherapy, antidepressants, or other psychotropic medications.

Recruitment Procedures

Describe settings where recruitment will occur

Subjects will be recruited from participation in IRB 7489.

How and by whom will subjects be approached and/or recruited?

The research assistant will notify a study clinician once a participant completing IRB 7489 is known to meet the selection criteria. The clinician will then approach the participant and discuss potential treatment in this protocol, with its attendant risks, benefits, and alternatives.

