How will the study be advertised/publicized?

There is no advertisement for this study other than what is undertaken in IRB 7489.

Do you have ads/recruitment material requiring review at this time?

No

Does this study involve a clinical trial?

Yes

Please provide the NCT Registration Number

04697693

Concurrent Research Studies

Will subjects in this study participate in or be recruited from other studies?

Yes

Describe concurrent research involvement

Potential participants in this open treatment study will have recently completed IRB 7489.

Inclusion/Exclusion Criteria

Name the subject group/sub sample

Depressed irb 7489 participants

Create or insert table to describe the inclusion criteria and methods to ascertain them

Inclusion criteria:

Method of ascertainment:

1. Individual has completed IRB 7489

1. Study records

2. Diagnosed with DSM 5 MDD

2. SCID, data from IRB 7489

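### Do the missing PTSD line in the inclusion lists and the unnamed pre-treatment visit leave the population and the baseline open?

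*Protocol*

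**What the plan says.** **Population.** The subject-population field of the Protocol (Description of Subject Population) reads "Participants in IRB 7489 with combined PTSD and MDD". The narrative list in the same section begins "1) participants in IRB 7489, (2) diagnosed with DSM 5 MDD", then gives the HRSD threshold and consent. The table under Inclusion/Exclusion Criteria is labelled "Depressed irb 7489 participants" and has four matching items. Neither list mentions PTSD. Under Recruitment Procedures, "The research assistant will notify a study clinician once a participant completing IRB 7489 is known to meet the selection criteria". The Background section says of the parent study: "A control group of 150 age-, sex-, and trauma exposure-matched subjects without PTSD are being recruited and assessed". The Lay Summary describes that comparison group in the words "relative to trauma-exposed healthy controls (TEHCs".

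**Baseline.** For the HRSD criterion the table gives the source as "3. Data from IRB 7489". The Lay Summary says: "Participants will be seen in person for the week 0 (baseline) visit, where they will complete baseline testing". It then describes Week 8 as a repeat of that testing. Study Procedures make Week 0 an in-person visit but do not list its measures. Item 4 there says that the Week 8 cognitive and physical tests are the ones given at the IRB 7489 baseline. The SAP plans paired t-tests of pre-to-post change in HRSD, NIH Toolbox total score and gait speed, and names no visit for the first value.

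**The concern.** **Population.** Completing IRB 7489 does not imply PTSD, because that study also recruits 150 controls without it. A control with MDD and an HRSD of 18 or more would pass every listed item. The research assistant flags candidates by the listed criteria, and with 20 completers one or two such entries would dilute the population the trial is about.

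**Baseline.** Patients are selected on a high HRSD. If that same score were the first value in the paired test, part of the later fall would be regression to the mean, and there is no control arm to remove it. The change in all three outcomes would also include untreated time between the parent study and the first dose, for which no maximum is set. Toolbox score and gait speed play no part in selection, so for those two only the untreated time would count. The wording about the IRB 7489 baseline in Study Procedures, item 4, makes this reading seem possible.

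**Working it through.** **1. Who would be enrolled.**
- For PTSD being required: the population field, which stands in the same section as the first list; Aim 1; and the SAP title.
- Against: silence in both lists and a group label that names depression only.
- Exposure: controls without PTSD who have MDD and an HRSD of at least 18. The protocol calls the controls healthy, so few if any should qualify, although no text says that MDD excludes a control.

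Nothing in the documents calls for enrolling people without PTSD.

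**2. Which value comes first in the paired test.**
- The Lay Summary labels Week 0 as baseline, places testing there, and has Week 8 repeat it.
- Study Procedures, item 3, has HRSD rated at the two-weekly contacts, and the Compensation section counts Week 0 among the biweekly visits. A Week 0 HRSD fits both.
- Study Procedures limit on-site attendance to what is necessary, yet Week 0 is on site, while later medication goes by courier. Dispensing alone does not obviously explain the visit; testing does.
- The Risks section offers a break halfway through the initial assessment, and lists screen shields for neuropsychological testing among the in-person precautions.
- Item 4 of Study Procedures identifies which tests make up the Week 8 battery. It does not say that IRB 7489 values are the comparator.
- The qualifying HRSD comes from IRB 7489 because eligibility screening is conducted under that protocol (Consent Procedures).

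**3. Size if the qualifying score were nevertheless reused.** The plan states no figure to reproduce here. Inputs: cut-off 18 and n = 20 from the protocol; mean 21, SD 7 and correlation 0.7 are assumptions. With no true change,

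fall = (1 − r) × SD × φ(z) / (1 − Φ(z)), where z = (cut-off − mean) / SD.

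- z = (18 − 21) / 7 = −0.429
- φ(z) = 0.364 and 1 − Φ(z) = 0.666, ratio 0.546
- 7 × 0.546 = 3.83
- fall = 0.3 × 3.83 = 1.15 points

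Simulation of the paired t-test with groups of 20 gives 15.2% rejection in the upper tail, against a nominal 2.5%.

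**4. The same with a Week 0 score as the first value.** Here fall = (r01 − r02) × SD × φ(z) / (1 − Φ(z)), where r01 and r02 are the correlations of the qualifying score with Week 0 and Week 8.
- Equal correlations: the fall is 0, and simulated rejection is 2.3% to 2.6% over the grid examined.
- Correlation decaying from 0.70 to 0.49: (0.70 − 0.49) × 3.83 = 0.80 points, 9.4% rejection. The qualifying score would give (1 − 0.49) × 3.83 = 1.95 points, 24.0% rejection.
- Share remaining: 0.21 / 0.51 = 41%.

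**5. Why the larger figures do not apply.** An extreme of 3.56 points and 45% rejection arises at mean 18.1, SD 9 and r = 0.5. But 18.1 is the mean of all PTSD participants, of whom 67.1% have MDD (Background). If the other 32.9% averaged 10 to 14 (assumed), the MDD mean would be:
- (18.1 − 0.329 × 14) / 0.671 = 20.1
- (18.1 − 0.329 × 10) / 0.671 = 22.1

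With SD 9 and r = 0.5 kept, rejection is then about 33% at mean 20 and 23% at mean 22. These figures also hold only if the qualifying score is reused.

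**The case for a change.** The strongest opposing case is that both gaps are literally there and cheap to close. The inclusion table is the working tool for recruitment, and it lacks the condition the trial studies. The SAP leaves the analyst a choice that should be closed before data are seen. Study Procedures name no Week 0 measure, and Week 0 is paid at $25, as for a virtual visit, against $100 for the Week 8 assessments. The payment therefore does not confirm that the Toolbox and gait tests are done at Week 0. The interval since IRB 7489 has no numerical limit.

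The textual facts stand. So does the point on payment: the evidence for a Week 0 HRSD is firmer than that for Toolbox and gait, which rests mainly on the Lay Summary. But the Lay Summary speaks of testing at baseline repeated at Week 8, and the Week 8 battery includes those tests, so the plain reading covers them. On the interval, participants are described as having recently completed the parent study, and the main plan is to consent them at its last visit. What does not stand is the step from missing detail to bias: no section names the parent-study score as the outcome baseline, and no wrongly enrolled patient is shown.

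**Conclusion.** No change to the plan is needed. Followed as a whole, the documents would enrol patients with both PTSD and MDD and compare Week 8 with Week 0. A PTSD line in the lists and a named visit in the SAP would record what the protocol already conveys; they would not alter who is treated or what is tested.

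The distortion of about 1.1 HRSD points (15% against 2.5% rejection) rests on an assumed mean, SD and correlation, and on using the qualifying score as the baseline, which the documents do not prescribe. Under the natural reading the bias is zero if the qualifying score correlates equally with Week 0 and Week 8. If the correlation decays as in the example, about 0.8 points and 9% rejection remain. That residue comes from selecting on an earlier score in a single-arm study, and naming the visit would not remove it.

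The conclusion rests on two readings: that the population field governs the lists, and that the Lay Summary's baseline testing includes HRSD, Toolbox and gait speed.
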